## **Study Protocol:**

The patients were inducted from the Out Patient Department of Endodontics in Baqai Dental College Hospital Karachi, Pakistan. A non-probability consecutive sampling was done and 120 patients were included and randomly divided in the 4 groups (n=30) using simple randomization as per the inclusion criteria. The study size was calculated with reference to previous reports, revealing that at least 30 individuals should be included as per the analysis of power of the study. The value of power used was 0.96, the effect size was taken as 0.4, and  $\alpha$  was set as 0.05. A verbal informed consent was taken from each participant before including them in a group.

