### **Exclusion criteria:**

- Patients who are pregnant and/or breastfeeding.
- Patients with reported allergy to diclofenac sodium, piroxicam, and tramadol.
- Patients with periodontal pathologies, necrotized pulp, ankylosed or resorbed roots, open apex and non-restorable tooth.
- Patients who have taken an analgesic in the past 24 hours.

The study was designed to be a double blinded study, where the operators and the patients both were unaware of the groups of drugs that were used; this anonymity was achieved by marking the groups A, B, C and D on boxes for drugs containing a placebo, diclofenac sodium, piroxicam, and tramadol respectively. The Heft Parker's visual analogue scale was used to assess

the patients' pain levels prior to the drug ingestion, and the study was continued on the patients that reported moderate to severe pain on the visual analogue scale. On this scale, the pain intensities were categorized as: no pain (0), mild pain (1-54 mm), moderate pain (55- 114 mm) and severe pain (> 114 mm). The patients were then given their respective group of drug where the control group received vitamin E (Evion, 400 mg) and three experimental groups received one tablet/capsule of diclofenac sodium (Voltral SR100, 100 mg), piroxicam (Feldene, 20 mg), and tramadol (Tramal, 50 mg). The patients were instructed to wait for 1 hour before they were administered inferior alveolar nerve block with 1.8 ml of 2% lidocaine with 1:100000 epinephrine using a non-aspirating syringe through a long needle of 27-Gauge. Standard root canal treatment was initiated after lip numbness was achieved, and pain levels were reassessed by Heft Parker's visual analogue scale during the root canal procedure. However, the patients who did not achieve the numbness of the lips were excluded from the study. Patients who reported discomfort and pain during the endodontic procedure were intervened appropriately; conversely, if the patient did not report any intraoperative pain, endodontic procedure was resumed.

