### **Statistical Analysis Plan:**

Test of normality was checked using one sample Shapiro Wilk. One-way ANOVA with Tukey's post-hoc will be employed if parametric test criteria is met; however, if the parametric criteria was not fulfilled, the experimental groups will be compared using Kruskal–Wallis test with post-hoc analysis. The Chi-square test will be used to compare gender and drug groups against the IANB efficacy. These aforementioned tests were conducted on SPSS Statistics version 25 (IBM Corp., Armonk, NY, USA).

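### Do exactly 30 patients per group under simple randomisation, and a power of 0.96 with no named test, call for a change to the plan?

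*Protocol*

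**What the plan says.** The Study Protocol section of the Protocol states that "120 patients were included and randomly divided in the 4 groups (n=30) using simple randomization". On size it says that "at least 30 individuals should be included as per the analysis of power of the study", and then "The value of power used was 0.96, the effect size was taken as 0.4", with alpha 0.05. No allocation mechanism, block, cap or list is described, and no test, endpoint or effect-size measure is attached to the power.

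The SAP plans two kinds of analysis and links neither to the sample size. For pain scores, "One-way ANOVA with Tukey's post-hoc will be employed if parametric test criteria is met", with Kruskal–Wallis as the fallback. For the success of the block, "The Chi-square test will be used to compare gender and drug groups against the IANB efficacy".

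The text under the Exclusion criteria heading of the Protocol adds a loss that occurs after allocation and dosing: "the patients who did not achieve the numbness of the lips were excluded from the study". No rate, allowance or replacement rule is given.

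**The concern.** Three features catch the eye.

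- **Allocation.** Simple randomisation, in its usual sense of an independent equal-probability draw for each patient, does not fix the arm sizes. Four arms of exactly 30 would be a rare accident. A reader judging the allocation would want to know whether a restricted list was used and not described.
- **Power.** The same 0.4 means different things as Cohen's f, w or d, and the power of 30 per group differs widely between them. If the figure belonged to a different test from the one planned, the trial could be much weaker than it claims.
- **Number analysed.** If 120 is the number allocated, the exclusions for lack of lip numbness leave fewer than 120 for analysis, and the stated power would be too high.

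At stake would be the credibility of the allocation and the adequacy of the sample size.

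**Working it through.** **Inputs.** From the Protocol: N = 120, four groups of 30, power 0.96, effect size 0.4, alpha 0.05. From the SAP: one-way ANOVA or Kruskal–Wallis, and chi-square. Assumed, because the documents give no figure: the proportion excluded for lack of lip numbness.

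**1. Reproduce the 0.96.** Read 0.4 as Cohen's f in a four-group one-way ANOVA. The noncentrality is λ = f²N = 0.16 × 120 = 19.2, with 3 and 120 − 4 = 116 degrees of freedom. The noncentral F distribution gives power 0.9643, which rounds to 0.96. At 29 per group (N = 116) it is 0.9583, so 30 per group is the smallest equal size that reaches 0.96. This also accounts for the words *at least 30*.

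**2. Try the other readings.**

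| Reading of 0.4 and 30 | Power | Fits 0.96 and a minimum of 30 per group? |
|---|---|---|
| f, ANOVA, 30 per group | 0.964 | Yes, on both counts |
| w, chi-square with 3 df, N = 120 | 0.970 | No: rounds to 0.97, and N = 114 already reaches 0.96 |
| d, two-group t test, 30 per group | 0.33 | No |
| f, ANOVA, 30 patients in total | 0.37 | No |

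Only the ANOVA reading, which is also a test the SAP names, matches both the rounded figure and the stated minimum.

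**3. Chance of equal arms.** Under unrestricted draws, P(30/30/30/30) = 120!/(30!⁴ × 4¹²⁰) = 0.000765, or about 1 in 1,308. Each arm has standard deviation √(120 × 0.25 × 0.75) = 4.74. In simulation the smallest arm averages 24.5 and the largest 35.7, and all four arms fall within 28 to 32 with probability 0.058. So either a restricted method was used and not described, or the term is used loosely. The text cannot settle which.

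**4. What unrestricted allocation would cost.** Averaging ANOVA power over 20,000 simple allocations of 120, for four patterns of group means at f = 0.4, gives 0.959 to 0.963, against 0.964 with equal arms. The loss is at most 0.9643 − 0.9586 = 0.006.

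**5. What the exclusions would cost.** If 120 is the number allocated and losses fall evenly across arms:

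| Analysed | Loss | ANOVA, f = 0.4 | Kruskal–Wallis, normal data |
|---|---|---|---|
| 120 | none | 0.964 | 0.954–0.956 |
| 115 | 5 patients | 0.957 | – |
| 108 | 10% (assumed) | 0.943 | 0.928–0.930 |
| 96 | 20% (assumed) | 0.912 | 0.891–0.895 |

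Five losses still round to 0.96. If 120 is already net of exclusions, the top row stands.

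**6. Would a blocked list gain anything?** With random losses of 10%, power is 0.935–0.941 under simple allocation and 0.942–0.943 under blocks. With 20% it is 0.901–0.907 and 0.909–0.910. The gain is below 0.01. Blocks also have a cost. With six blocks of 8 and six of 12, an operator who saw every letter and knew the sizes and order of the blocks could predict (6 × 8/7 + 6 × 1.2)/120 = 14.06/120 = 11.7% of allocations with certainty. Knowing the sizes but not the order, the figure is about 6% by simulation. Under simple randomisation it is zero.

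**The case for a change.** The best case for acting is that correction costs only wording and the gaps are real. Equal arms at 1 in 1,308 mean that the stated method is probably not the one used, and the method bears on how far the allocation can be trusted. The power statement names no test, and a chi-square with w = 0.4 comes within a point of 0.96, so reproducing the figure is not proof of what was intended. Under the ANOVA reading, 120 is the smallest balanced total that reaches 0.96, so nothing is held back for patients dropped after dosing. An unlabelled 0.96 could also be taken as the power of each drug-versus-placebo comparison, which it is not.

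Most of this stands as a comment on description. The allocation mechanism should be known to a reader, 0.96 is an upper figure if 120 is the number allocated, and it is an omnibus figure only. Three parts do not carry further:

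- The chi-square fails both the rounding check and the minimum-size check, and a total of 30 contradicts the stated n of 30 in each of four groups. Neither is a serious rival to the ANOVA reading.
- The improbability of equal arms is a matter of chance and terminology, not a flaw in the comparison. Simple and restricted randomisation both support the planned tests, and those tests accept unequal groups.
- The Protocol describes inclusion and division in the past tense, so allocation appears complete. A new list would then be moot, and by step 6 it would gain almost nothing.

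**Conclusion.** No change to the plan follows. The sample-size figure is sound on its natural reading: omnibus one-way ANOVA, Cohen's f = 0.4, alpha 0.05, 30 per group, power 0.964. That f is the measure meant is an inference, supported by both the rounding and the minimum group size. The mismatch between simple randomisation and four arms of 30 is most likely loose wording or an undescribed restricted list. Taken literally, it costs at most 0.006 of average omnibus power. Exclusions would bring ANOVA power to 0.943 or 0.912 under assumed losses of 10% or 20%, and would cost nothing if 120 is net of them, so no shortfall has been shown.

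What remains is detail that analysts and authors fill in sensibly when reporting: how allocation was done, which test the power refers to, and the numbers allocated, excluded and analysed in each arm. Two matters lie outside this conclusion: the power of individual drug-versus-placebo comparisons, and whether patients without lip numbness belong in the analysis set. The power statement settles neither.

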### **Inclusion Criteria:**

- Patients between the ages of 18 - 65 years.
- Patients with no medical or systemic conditions.
- Patients with prolonged pain response on cold pulp testing of 1st and 2nd mandibular molars.
- Patient with 1st and 2nd mandibular molars having symptomatic irreversible pulpitis with no periapical pathology or tenderness on percussion.
- Preoperative moderate to severe pain on Heft Parker's visual analogue scale.
- Patients who can understand the recording of the pain using Heft Parker's visual analogue scale.

### **Exclusion criteria:**

- Patients who are pregnant and/or breastfeeding.
- Patients with reported allergy to diclofenac sodium, piroxicam, and tramadol.
- Patients with periodontal pathologies, necrotized pulp, ankylosed or resorbed roots, open apex and non-restorable tooth.
- Patients who have taken an analgesic in the past 24 hours.

The study was designed to be a double blinded study, where the operators and the patients both were unaware of the groups of drugs that were used; this anonymity was achieved by marking the groups A, B, C and D on boxes for drugs containing a placebo, diclofenac sodium, piroxicam, and tramadol respectively. The Heft Parker's visual analogue scale was used to assess

the patients' pain levels prior to the drug ingestion, and the study was continued on the patients that reported moderate to severe pain on the visual analogue scale. On this scale, the pain intensities were categorized as: no pain (0), mild pain (1-54 mm), moderate pain (55- 114 mm) and severe pain (> 114 mm). The patients were then given their respective group of drug where the control group received vitamin E (Evion, 400 mg) and three experimental groups received one tablet/capsule of diclofenac sodium (Voltral SR100, 100 mg), piroxicam (Feldene, 20 mg), and tramadol (Tramal, 50 mg). The patients were instructed to wait for 1 hour before they were administered inferior alveolar nerve block with 1.8 ml of 2% lidocaine with 1:100000 epinephrine using a non-aspirating syringe through a long needle of 27-Gauge. Standard root canal treatment was initiated after lip numbness was achieved, and pain levels were reassessed by Heft Parker's visual analogue scale during the root canal procedure. However, the patients who did not achieve the numbness of the lips were excluded from the study. Patients who reported discomfort and pain during the endodontic procedure were intervened appropriately; conversely, if the patient did not report any intraoperative pain, endodontic procedure was resumed.

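### Patients without lip numbness are dropped after randomisation, study drug and block, so the test of drug group against IANB efficacy is not the comparison as randomised

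*Protocol*

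**What the plan says.** The order of events can be read directly from the Protocol.

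- Study Protocol section: "120 patients were included and randomly divided in the 4 groups (n=30) using simple randomization".
- Text under Exclusion criteria: the study drug is taken first, and "The patients were instructed to wait for 1 hour before they were administered inferior alveolar nerve block".
- Same text: "Standard root canal treatment was initiated after lip numbness was achieved". Pain is then scored again on the Heft Parker "visual analogue scale during the root canal procedure".
- Same text: "the patients who did not achieve the numbness of the lips were excluded from the study".
- Same text, on blinding: "The Chi-square test will be used to compare gender and drug groups against the IANB efficacy" is the SAP's later test of the result, while on conduct the Protocol says that "the operators and the patients both were unaware of the groups of drugs that were used".

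The SAP says little more on this point. Besides the chi-square test of efficacy just quoted, it plans a one-way ANOVA with Tukey's test, or Kruskal–Wallis if parametric conditions fail, without naming the variable. It names no analysis set, does not define IANB efficacy, gives no rule for patients without numbness, and does not ask for their number by arm.

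On size, the Study Protocol section says that "at least 30 individuals should be included as per the analysis of power of the study", with power 0.96, effect size 0.4 and alpha 0.05.

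**The concern.** Lip numbness is not an eligibility criterion. It appears in neither the inclusion nor the exclusion list, and it cannot be known until both the study drug and the block have been given. Removing patients on that basis gives up the protection of randomisation: the groups compared are those who were randomised and then became numb.

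This bears directly on the endpoint. The SAP tests drug group against IANB efficacy, and numbness is the Protocol's own sign that treatment may begin after the block. Because efficacy is undefined, two readings are open.

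- **Reading (a): success requires a numb lip.** The excluded patients are then block failures that have been left out.
- **Reading (b): efficacy is judged only among numb patients.** The excluded patients then have no outcome, and the numb patients in different arms need not be alike.

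Under either reading, the numb-only test could hide, understate or overstate a difference between the randomised groups. Since numbness by arm is not to be reported, a reader could not tell.

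**Working it through.** **The plan's own figure.** Inputs from the Study Protocol section: 4 groups, 120 patients, effect size 0.4 (type not named; taken as Cohen's f), alpha 0.05. For a one-way ANOVA, the noncentrality is f² × N = 0.16 × 120 = 19.2 on 3 and 116 degrees of freedom, which gives power 0.964. The stated 0.96 is reproduced with all 120 analysed. If 10% or 20% were excluded (assumed rates), 108 or 96 would remain and power would be 0.943 or 0.912. That is a modest loss of precision. The selection problem is separate.

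**Selection: inputs.** The documents give no numbness or success rates. Every rate below is an assumption chosen to show the mechanism.

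**Reading (a).** Success among all randomised = numbness × success among numb patients.

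| Assumed numbness | Assumed success among numb | Numb-only difference | Success as randomised | Difference as randomised |
|---|---|---|---|---|
| 95% v 90% | 50% v 50% | 0 | 0.95 × 0.50 = 47.5% v 0.90 × 0.50 = 45.0% | 2.5 points |
| 95% v 85% | 50% v 50% | 0 | 47.5% v 0.85 × 0.50 = 42.5% | 5.0 points |
| 95% v 80% | 50% v 50% | 0 | 47.5% v 0.80 × 0.50 = 40.0% | 7.5 points |
| 80% drug v 90% control | 45% v 40% | 5 points for drug | 0.80 × 0.45 = 36% v 0.90 × 0.40 = 36% | 0 |
| 90% v 90% | 60% v 40% | 20 points | 0.90 × 0.60 = 54% v 0.90 × 0.40 = 36% | 18 points |

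The first three rows hide a difference, the fourth creates one, and the last shows that equal numbness changes little.

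**Reading (b).** Suppose 80% of patients would be numb in either arm, with 50% success whichever arm they are in. Suppose the drug makes a further 15% numb, and these have 20% success.

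- Control, numb-only: 50.0%.
- Drug, numb-only: (0.80 × 0.50 + 0.15 × 0.20) / 0.95 = 0.430 / 0.95 = 45.3%.
- Apparent effect: the drug looks 4.7 points worse, although it changes nothing in patients who are numb either way.

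If the further 15% have 35% success, the drug arm shows 0.4525 / 0.95 = 47.6%, a false gap of 2.4 points. If they have 50% success, the gap is zero.

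**Scale.** At 30 per arm and 50% success, the standard error of a two-arm difference is √(0.25/30 + 0.25/30) = 0.129, about 13 points. For success of 40% in control and 47.5% in each of three arms, the mean is 45.625%. The noncentrality is 30 × (0.05625² + 3 × 0.01875²) / (0.45625 × 0.54375) = 0.510. On 3 degrees of freedom, the four-arm chi-square then has power 0.082.

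**The case against.** The strongest reply has five parts.

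1. **Numb-only efficacy is a legitimate question.** Adjunct analgesia given a working block may be what the investigators want to know, and the documents do not rule it out. This stands in part, which is why the numb-only analysis should be kept. But the plan neither states that question nor labels the result as conditional.
2. **Blinding protects.** Operators and patients did not know the drug, so selective judgement of numbness is unlikely. That stands, and a reader should not infer that patients were removed because of their arm. Blinding does not, however, make numbness itself equal across arms.
3. **The harm is hypothetical and small.** The illustrated distortions run from 0 to 7.5 points, against a standard error of about 13 points, and the trial would rarely detect even the largest. This stands as to size. It does not justify a systematic error that is cheap to avoid and that a larger sample would not remove.
4. **The variable for the ANOVA is not named.** This stands. Intraoperative pain is likely, but pain is also scored before the drug, and a comparison of those scores would not depend on numbness in the same way. The point is firm for the chi-square and conditional for the other test.
5. **The sample size looks ambiguous.** A reader might infer that 30 per group could be a count after exclusion, or that the power calculation is wrong. The documents support neither: 30 per group is stated at randomisation, and the power reproduces. Only whether excluded patients were replaced is left open.

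**Conclusion.** The concern holds in a limited form. It is certain from the text that the exclusion follows randomisation, drug and block, and that the SAP does not undo it; so the efficacy chi-square, carried out as written, is not the comparison as randomised. The same applies to the ANOVA or Kruskal–Wallis test if its variable is intraoperative pain.

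A reader might go further and infer that the results are biased, or biased towards the active drugs. The documents do not support that. Bias needs numbness, or the mix of patients who become numb, to differ by arm, and they neither show nor exclude this. The illustrations point in both directions and rest wholly on assumed rates. This should be fixed because the rule can give a wrong answer that nobody could detect, not because a wrong answer has been shown.

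**What to change.** **Protocol, text under Exclusion criteria.** Reword the sentence so that absence of lip numbness does not remove a patient from the efficacy analysis. Patient management stays as it is.

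**SAP.**
- Define IANB efficacy.
- Run the main chi-square on all randomised patients in their assigned arm, with absence of lip numbness counted as no successful block. State how any patient randomised but not dosed is handled.
- Report numbness and exclusions by arm, and give the numb-only chi-square beside the main one.
- Name the variable for the ANOVA or Kruskal–Wallis test. If it is intraoperative pain, label the comparison as conditional on numbness, since pain during treatment cannot be scored where treatment was not started. A Kruskal–Wallis test with non-numb patients tied at the worst rank is optional.
- State whether excluded patients were replaced.

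**Cost and limits.** One reworded sentence, a short SAP paragraph, one table row and one extra chi-square; no added patients, visits or procedures. Technically missed blocks will add some noise to the main analysis, and the numb-only result beside it shows how far that matters. The change restores the randomised comparison for the binary outcome only, and it adds no power. It also needs the arm and numbness status of each excluded patient. The Protocol is written in the past tense and does not say that these were kept. If they were not, report the chi-square, and the pain comparison if that is the variable, as conditional on numbness.

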### **Statistical Analysis Plan:**

Test of normality was checked using one sample Shapiro Wilk. One-way ANOVA with Tukey's post-hoc will be employed if parametric test criteria is met; however, if the parametric criteria was not fulfilled, the experimental groups will be compared using Kruskal–Wallis test with post-hoc analysis. The Chi-square test will be used to compare gender and drug groups against the IANB efficacy. These aforementioned tests were conducted on SPSS Statistics version 25 (IBM Corp., Armonk, NY, USA).

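### Pre-drug pain score is recorded but no planned analysis is specified to use it: an optional, low-severity efficiency gain, not an error

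*SAP*

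**What the plan says.** The procedures text that follows the Protocol's exclusion criteria has two pain measurements on the same scale. The first is taken before the drug and decides who goes on: "pain levels prior to the drug ingestion, and the study was continued on the patients that reported moderate to severe pain". The entry bands are "moderate pain (55- 114 mm) and severe pain (> 114 mm"), so continuing patients score at least 55 mm. The second comes after the nerve block: "pain levels were reassessed by Heft Parker's visual analogue scale during the root canal procedure". Between the two, "the patients who did not achieve the numbness of the lips were excluded from the study".

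The Protocol's opening section says patients were "randomly divided in the 4 groups (n=30) using simple randomization", with no stratification by pain mentioned. On sample size it says "The value of power used was 0.96, the effect size was taken as 0.4", with alpha 0.05.

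The SAP is one paragraph. It gives a normality check, then "One-way ANOVA with Tukey's post-hoc will be employed if parametric test criteria is met"; otherwise, "if the parametric criteria was not fulfilled, the experimental groups will be compared using" Kruskal-Wallis with a post-hoc step. A chi-square test relates gender and drug group to IANB efficacy. The SAP names no outcome for ANOVA or Kruskal-Wallis, and no covariate, change score or baseline-adjusted model.

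**The concern.** A baseline measurement of the outcome is often the most useful covariate in a small parallel-group trial, and here every continuing patient has one. If the ANOVA outcome is intraoperative HP-VAS, the only continuous measure described after the drug, any variation that baseline pain explains stays in the error term. The pairwise Tukey comparisons, which answer the drug-versus-placebo question, are then less precise than the collected data allow.

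The amount at stake depends entirely on the within-group correlation r between the two scores. Two design features may lower it: the 55 mm floor narrows the range of baseline scores, and only patients with lip numbness are scored during treatment. The gain could therefore be close to nothing.

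**Working it through.** **Inputs.** From the Protocol's opening section: N=120, k=4 groups, n=30 each, effect size 0.4, alpha 0.05, power 0.96. Assumptions: 0.4 is Cohen's f (its type is not stated); all 30 per arm are analysed; r is 0.1 to 0.5.

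**1. The plan's own figure.** For the omnibus F test, df = 3 and 116, and the noncentrality is N·f² = 120 × 0.16 = 19.2. Power is 0.964. The stated 0.96 reproduces, which supports reading 0.4 as f.

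**2. One Tukey pair, unadjusted.** If two groups lie 0.4 SD above the grand mean and two lie 0.4 SD below, f=0.4 and a pair from opposite sides differs by d=0.8. The noncentrality is d·√(n/2) = 0.8 × √15 = 3.098. The Tukey critical value on the t scale is 2.607 (df 116). Power is 0.688.

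**3. Effect of the covariate.** A common-slope ANCOVA takes the error df from 116 to 115. Relative to the unadjusted analysis, the expected variance of a pairwise contrast is

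V = (1 − r²) × (1 + 1/(N − k − 2)) = (1 − r²) × (1 + 1/114).

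The second factor is the cost of estimating the slope. Tukey power uses noncentrality 3.098/√V, and omnibus power uses 19.2/V, both with error df 115.

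| r | V | Tukey power, d=0.8 | Omnibus power, f=0.4 |
|---|---|---|---|
| unadjusted | 1 | 0.688 | 0.964 |
| 0 | 1.009 | 0.683 | 0.963 |
| 0.1 | 0.999 | 0.689 | 0.9645 |
| 0.2 | 0.968 | 0.705 | 0.969 |
| 0.3 | 0.918 | 0.733 | 0.976 |
| 0.5 | 0.757 | 0.828 | 0.992 |

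The ratio of interval widths is close to √V: 1.0044 at r=0 (about 0.45% wider once the df change is counted), 0.958 at r=0.3 and 0.870 at r=0.5. A simulation of 40,000 trials per setting gave contrast-variance ratios of 1.0095, 0.920 and 0.758 at r=0, 0.3 and 0.5, in line with the formula.

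**4. Break-even.** Setting V=1 gives r = √(1/(N − k − 1)) = √(1/115) = 0.093. If exclusions for lack of lip numbness left only 80 patients (an assumed figure), it would be √(1/75) = 0.115.

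**5. Non-normal scores.** Intraoperative pain after a working block may be skewed with many zeros. A simulation of 4,000 trials per setting assumed 34% zeros, a skewed scale, and placebo against three equal drugs:

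| r | ANOVA | ANCOVA | Kruskal-Wallis | Rank ANCOVA |
|---|---|---|---|---|
| 0.2 | 0.68 | 0.68 | 0.82 | 0.83 |
| 0.3 | 0.67 | 0.69 | 0.80 | 0.84 |
| 0.5 | 0.67 | 0.74 | 0.80 | 0.90 |

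Under this assumed shape, linear ANCOVA does worse than the existing Kruskal-Wallis fallback at each r. The fallback should therefore stay, and any gain there has to come from a rank-based adjustment.

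**The case against.** The strongest reply is that nothing here is broken. The planned tests are valid, the omnibus power is already 0.964, and r is unknown and may be low. The outcome is also inferred: because the SAP names none, a change score, which would use the pre-drug value, is not excluded. If Shapiro-Wilk sends the data to Kruskal-Wallis, a linear ANCOVA would never run. The SAP lists tests and promises no intervals, so wider intervals are not a failure of anything planned. All of this stands. It limits the point to an optional refinement under a stated reading.

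One part is weaker than it looks. The 0.964 matches the omnibus test, whereas a single Tukey pair at the same planning effect, with the two-against-two split, has power 0.688. There is room for improvement where the drug-placebo question is answered.

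A reader might go further and infer that simple randomization without adjustment leaves the comparison biased by chance differences in baseline pain. The documents do not support that. Chance imbalance is already inside the unadjusted standard error and type I error; it is the same efficiency loss seen from another side and must not be counted as a second harm. Nor does the missing covariate make the sample-size statement wrong, since that figure reproduces.

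Timing also matters. The Protocol is written in the past tense and the SAP mixes past and future, so the documents do not settle whether outcome data had been analysed. A covariate added after that would be post hoc.

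**Conclusion.** The point holds as a low-severity, optional efficiency gain. No analysis in the SAP is specified to use the pre-drug HP-VAS, and using it would cost almost nothing. The benefit is negligible at r=0.1, small at 0.2 to 0.3 (2 to 5 percentage points of pairwise power) and material only at 0.5 (14 points).

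This rests on four assumptions: intraoperative HP-VAS is the outcome of ANOVA/Kruskal-Wallis; 0.4 is Cohen's f; 30 per arm are analysed; and the power figures apply to roughly normal scores with a common slope. The documents do not support calling the unadjusted analysis invalid, biased or underpowered against its own stated target. The chi-square analysis of IANB efficacy is not affected.

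**What to change.** - **Outcome.** State that the ANOVA/Kruskal-Wallis comparison is of intraoperative HP-VAS, if that is what is meant.
- **Parametric branch.** Replace one-way ANOVA with ANCOVA of intraoperative HP-VAS on drug group, with baseline HP-VAS as covariate and Tukey-adjusted pairwise comparisons. Check normality on the model residuals.
- **Non-parametric branch.** Keep Kruskal-Wallis with its post-hoc. Add a baseline-adjusted rank ANCOVA (Quade) with multiplicity-adjusted pairwise comparisons of the rank residuals. This gives tests, not differences in mm.
- **IANB efficacy.** Leave the chi-square analysis unchanged.
- **Timing.** If outcome data have already been analysed, report the adjusted model as a labelled additional analysis beside the planned one.

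The cost is a few lines of SAP text, one of 116 residual degrees of freedom (intervals about 0.45% wider if r=0) and slightly more analysis work. No new measurement, visit or patient is needed.

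### Block success (IANB efficacy) gets only a chi-square across drug groups, with no drug-versus-placebo comparison; no planned analysis includes an effect estimate

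*SAP*

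**What the plan says.** The SAP is one paragraph under the heading Statistical Analysis Plan. It has two alternative branches that depend on a normality check. In the first, "One-way ANOVA with Tukey's post-hoc will be employed if parametric test criteria is met". In the second, "the experimental groups will be compared using Kruskal–Wallis test with post-hoc analysis". One sentence then covers the block outcome: "The Chi-square test will be used to compare gender and drug groups against the IANB efficacy". That sentence also plans a comparison by gender, which is not a treatment contrast. Nothing follows on which arms are compared in pairs, how multiplicity is handled, or what measure of effect is reported.

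The Protocol text below the exclusion list describes blinding by "marking the groups A, B, C and D on boxes for drugs containing a placebo, diclofenac sodium, piroxicam, and tramadol respectively", and calls the placebo arm the control. It grades pain as "no pain (0), mild pain (1-54 mm), moderate pain (55- 114 mm) and severe pain (> 114 mm", and separately notes that "if the patient did not report any intraoperative pain, endodontic procedure was resumed". It does not say which of these is IANB efficacy. It also states that "the patients who did not achieve the numbness of the lips were excluded from the study"; this happens after the study drug has been taken.

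On sample size, the Protocol section Study Protocol says: "The value of power used was 0.96, the effect size was taken as 0.4", with alpha 0.05 and 30 patients in each of four groups.

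**The concern.** With placebo as one of the four labelled groups, the chi-square reads as a test of four success rates on 3 degrees of freedom. A significant result says only that the four rates are not all equal. It gives no role to placebo, no direction and no size.

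If the aim is to learn which premedication improves the block, the analysis of block success stops one step short. A report that followed the plan could claim a difference between groups but could not name the drug or say how large its benefit is. Any later choice of pairs, and of adjustment, would be made with the results in view.

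**Working it through.** **1. The plan's own figure.** Inputs from the Protocol: four groups, N=120, effect size 0.4, alpha 0.05. The effect-size metric is not named; I take it as Cohen's f. For a four-group ANOVA the noncentrality is f² × N = 0.16 × 120 = 19.2. With 3 and 116 degrees of freedom the critical F is 2.68, and power is 0.964. This reproduces the stated 0.96. A 3-df chi-square with w=0.4 gives 0.970, also close. A two-group comparison with 30 per group does not reproduce it: d=0.4 gives 0.34 and d=0.8 gives 0.87. The stated power therefore fits an overall test and not a drug-versus-placebo contrast.

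**2. The overall test ignores which arm is placebo.** For equal arms, chi-square = Σ(xᵢ − 30p)² / [30p(1 − p)], where p is the pooled success rate. The counts are illustrative, because the documents give no success rates.

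- Counts 9, 9, 9, 18: p = 45/120 = 0.375 and the expected count is 11.25. Chi-square = (3 × 2.25² + 6.75²) / (30 × 0.375 × 0.625) = 60.75 / 7.031 = 8.64, p=0.034.
- If the 18 is a drug, that drug is (18 − 9)/30 = 30 points above placebo. If the 18 is placebo, all three drugs are 30 points below it. The planned result is the same in both cases.

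**3. A significant overall test with no drug differing from placebo.** Placebo 14, drugs 8, 14 and 20.

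- Overall: p = 56/120 = 0.467, expected count 14. Chi-square = (6² + 6²) / (30 × 0.467 × 0.533) = 72 / 7.467 = 9.64, p=0.022.
- Each drug against placebo, Pearson without continuity correction: p=0.11 (8 v 14), p=1.00 (14 v 14), p=0.12 (20 v 14). The significance comes from the gap between two drugs, 8 v 20.

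**4. How often this happens.** Simulation with 400,000 trials per scenario, 30 per arm and placebo assumed at 30%. The table shows the share of significant overall tests in which no drug is significantly better than placebo.

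| Assumed rates on the drugs | Contrasts unadjusted at 0.05 | Contrasts with Holm |
|---|---|---|
| All three at 60% | about 0.1% | 1.4% |
| One at 80%, two at 30% | 1.2% | 4.4% |
| One at 60%, two at 30% | 15% | 35% |

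**5. Power of the missing contrasts.** At an assumed 30% v 60% with 30 per arm, power per contrast is 66% unadjusted. With Holm it is 46% when only one drug works and 55% when all three do.

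**The case against.** The strongest reply is that the documents available state no objective, hypothesis or primary endpoint. The pain score may be the main analysis, and its Tukey branch already compares each drug with placebo. That stands. The purpose given here is an inference from the design, and the consequence is confined to the block-success outcome. A reader might infer that the trial as a whole cannot compare any drug with placebo; the documents do not support that.

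A reader might also infer that the missing effect estimate is peculiar to IANB efficacy. It is not: neither pain-score branch plans an estimate or interval. The Kruskal–Wallis post-hoc method is unnamed, and that branch speaks of the experimental groups, a term the Protocol uses for the three drugs apart from the control. Only the missing post-hoc step is specific to IANB efficacy.

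A third inference is that the plan inflates the false-positive rate. It does not: a single overall test has no multiplicity error of its own. Inflation would arise only if unadjusted contrasts were added later, and nobody has planned that.

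Finally, the 15% and 35% figures come from one scenario, with a single drug of moderate effect. With three effective drugs, or one very effective drug, the mismatch is rare. The range should be quoted and not its upper end. The two worked tables are also constructed: they show what the test can and cannot distinguish, not what is likely.

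**Conclusion.** The concern holds in limited form. For block success the SAP plans an overall test and nothing that identifies a drug or measures its benefit, although the same paragraph gives both pain-score branches a follow-up step. The test is valid but does not answer the question the placebo arm appears to pose.

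The logical gap (steps 2 and 3) does not depend on guessed success rates. Its practical frequency does: about 0.1% to 15% of significant overall results unadjusted, and 1.4% to 35% after Holm, over the three assumed scenarios. The reading rests on placebo being one of the groups in the chi-square. If it were left out, there would be no comparison with placebo at all.

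**What to change.** After the chi-square sentence, add:

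> Each active drug is compared with placebo on IANB success (three contrasts) by Pearson chi-square, or Fisher's exact test if an expected count is below 5, with Holm-adjusted p-values at family-wise 0.05, and by risk difference with confidence intervals (Newcombe; multiplicity-adjusted where used for claims). Drug-versus-drug comparisons are exploratory.

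The four-arm chi-square may stay as the overall test. Adjusted comparisons of all pairs, in line with the Tukey branch, would also be defensible; three contrasts spend less of the limited power.

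Two inputs must be settled for the contrasts to be reproducible. State which of the Protocol's pain outcomes defines IANB success, and report by arm the patients excluded for lack of lip numbness.

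The documents mix future and past tense, so the work may already be done. If the data have been analysed, label the contrasts post hoc.

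The cost is wording only, with no new data. The drawback is power: adjustment lowers it from 66% to 46% per contrast in the one-drug scenario above. The report should say that the stated 0.96 fits an overall test and does not apply to these contrasts.
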